**Comparator Arms:**

- Interruptive reminder group: Providers will receive education via a pop-up alert at the time that the chart is opened for eligible patient visits assigned to the interruptive reminder group.
- Non-interruptive reminder group: Providers will be able to seek out education at their own initiative via an on-demand reminder within a section of the chart for eligible patient visits assigned to the non-interruptive reminder group.
- The reminder will have the same format for both groups, but the manner in which it is displayed will differ between the two groups (i.e., interruptive vs. non-interruptive.)
- The reminder will alert clinicians that a statin is recommended for the patient and list the reasons the statin is indicated. It will give the clinicians a defaulted option for statin prescription as well as alternatives. If the clinician accepts the alert, an order for a statin will be placed in their “shopping cart” for convenience, and the order can be signed to prescribe the medication. If the clinician does not wish to prescribe a statin from the reminder, they can choose an acknowledgement reason.
- No reminder group: No alert recommending a statin will be displayed/available to the provider. The system will record eligibility through triggering a “silent” BPA, which is not displayed to the clinician and exists solely for data collection purposes.

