# 8.0 Data Collection:

## 8.1 Outcomes:

**Primary Effectiveness Outcome:** The primary outcome is statin prescription within 24 hours of BPA firing.

This outcome will be measured within the first 24 hours after the interruptive, non-interruptive, or silent BPA is fired. Only prescriptions for statins which are signed by the provider, and not canceled, will be included in this measurement.

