### 8.4 Outcome Data:

Primary Outcome: All statin prescriptions signed in the first 24 hours after intervention.

Secondary Outcome: All statin prescriptions signed in the first 365 days after intervention. All LDL-C values resulting from samples collected after intervention and during study period.

Exploratory Outcome: Ezetimibe, PCSK9 inhibitor, or bempedoic acid prescriptions signed in the first 365 days after the intervention. Filling of statin prescriptions within 365 days after the intervention. New ASCVD events recorded within 365 days after the intervention. Date and time of statin prescription signing within 365 days after the intervention.

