No alert recommending a statin will be displayed/available to the provider. The system will record eligibility through triggering a "silent" alert, which is not displayed to the clinician and exists solely for data collection purposes.

PI: [name], MS

[figure not shown]

Figure 1: Schematic procedure of arm assignment and enrollment.

Both the interruptive and the non-interruptive alerts will have the same format; only the manner in which it is displayed will differ. The reminder will alert clinicians that a statin is recommended for the patient and list the reasons the statin is indicated. It will give the clinicians a defaulted option for statin prescription as well as alternatives. If the clinician accepts the alert, an order for a statin will be placed in their "shopping cart" for convenience, and the order can be signed to prescribe the medication. If the clinician does not wish to prescribe a statin from the reminder, they can choose an acknowledgement reason.

Endpoints

Primary Endpoint

The primary outcome will be a binary outcome of statin prescription placed within 24 hours after enrollment BPA firing (interruptive, non-interruptive, or no reminder) (Yes/No).

Secondary Endpoints

This trial has two secondary outcomes:

- 1. A binary outcome of statin prescription placed within 12 months after enrollment BPA firing (Yes/No)
- 2. The patient's first LDL-C level measured during the follow-up between 30 days and 12 months since the enrollment visit.

PI: [name], MS

Exploratory Endpoints

- 1. A binary outcome of any non-statin lipid lowering agent prescription placed within 12 months after enrollment BPA firing (ezetimibe, PCSK9 inhibitor, or bempedoic acid) (Yes/No)
- 2. A binary outcome of any statin prescription filled within 12 months of enrollment BPA firing (Yes/No)
- 3. A binary outcome of new ASCVD event within 12 months of enrollment BPA firing (Yes/No)
- 4. Time from enrollment BPA firing to statin prescription

Statistical Approach

Target Population

The target population of the estimand will be the principal stratum that includes all participants meeting the above inclusion/exclusion criteria, for whom the randomization allocated by the EHR embedded tool is executed.

Analysis Dataset

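### The protocol counts only statin prescriptions signed and not canceled for the primary endpoint, but the SAP says placed and carries over neither condition; the two should be aligned

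*SAP*

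**What the plan says.** The primary endpoint is described in three places, with different conditions.

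- **Protocol 8.1 (Outcomes)** sets the window, "This outcome will be measured within the first 24 hours after the interruptive, non-interruptive, or silent BPA is fired", and then the counting rule: "Only prescriptions for statins which are signed by the provider, and not canceled, will be included in this measurement".
- **Protocol 8.4 (Outcome Data)** lists the data as "All statin prescriptions signed in the first 24 hours after intervention". Signing is kept; cancellation is not mentioned.
- **SAP, Endpoints (Primary Endpoint)** says "The primary outcome will be a binary outcome of statin prescription placed within 24 hours after enrollment BPA firing". The SAP's Analysis Dataset section uses the same verb, and its primary-analysis paragraph refers only to a statin prescription within 24 hours. No SAP endpoint definition mentions signing or cancellation.

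The SAP also uses *placed* for an earlier step. In its Interventions section the verb describes the unsigned cart order: "If the clinician accepts the alert, an order for a statin will be placed in their" (the sentence goes on to name the cart, and makes signing the step that prescribes). The protocol's Comparator Arms text has the same sentence.

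Protocol 8.3 plans to collect whether the reminder was accepted, and the date, time and dose of lipid-lowering prescriptions. Neither 8.3 nor 8.4 lists order status or a cancellation time.

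**The concern.** The primary endpoint is a Yes/No classification of each patient, so both documents must give the same answer for the same order. As written, a programmer working from the SAP has no instruction to remove canceled orders, and one working from Protocol 8.1 does.

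The mismatch might not be neutral between arms. Only the alerts pre-load a default statin order; the control arm sees no alert. Under Protocol 7.3 the interruptive alert appears when the chart is opened and must be accepted or acknowledged before the clinician goes on, while Protocol 6.4 leaves the prescribing decision to the clinician in discussion with the patient. An order accepted early and then withdrawn is a plausible path in the interruptive arm, with no alert-driven counterpart in control.

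Two features raise the stakes. Clinicians and investigators are not blinded (Protocol, Blinding), so the rule is best fixed before outcomes are extracted. The estimated prescribing rates also drive the interim conditional power and sample-size re-estimation (Protocol 12.0), so the definition affects the final sample size as well as the final test.

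**Working it through.** **Step 1. Classify the same order under each text.**

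| Order history | Protocol 8.1 | Protocol 8.4 | SAP |
|---|---|---|---|
| Signed at hour 1, kept | Yes | Yes | Yes |
| Signed at hour 1, canceled at hour 5 | No | Yes | Yes, read literally |
| Signed at hour 1, canceled months later | Yes if the 24-hour window governs; No if status is read at extraction | Yes | Yes, read literally |
| Alert accepted, cart order never signed | No | No | Probably No; *placed* leaves doubt |

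The second row is a direct conflict. The third is a missing assessment time. The fourth is a lesser ambiguity.

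**Step 2. Reproduce the plan's own figure.** Inputs from the SAP, Sample Size Considerations: control 3%, interruptive 6%, 90% power, type I error 0.05 (taken as two-sided). With pooled null variance and no continuity correction:

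n per arm = [1.96·√(2·0.045·0.955) + 1.2816·√(0.03·0.97 + 0.06·0.94)]² / 0.03² = (0.5746 + 0.3747)² / 0.0009 ≈ 1,001.4, rounded up to 1,002 per arm and 3,006 in total. This matches the plan. Power at 1,000 per arm is 90.0%.

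**Step 3. Unequal miscount under a true null.** The documents give no unsigned or canceled rates, so the extra share e is an assumption. Retained prescriptions are 3% in both arms, and the interruptive arm has e further orders that a literal *placed* rule would count. With p₁ = 0.03, p₂ = 0.03 + e and p̄ their mean:

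Chance of significance = Φ{[e − 1.96·√(2p̄(1−p̄)/n)] / √[(p₁(1−p₁) + p₂(1−p₂))/n]}

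For e = 0.01 and n = 1,000: (0.01 − 0.01611)/0.00822 = −0.74, so Φ = 0.229. OR = (0.04/0.96)/(0.03/0.97) = 1.35.

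| e (points) | Share of counted interruptive-arm orders | OR | 1,000 per arm | 2,000 per arm |
|---|---|---|---|---|
| 0.5 | 0.5/3.5 = 14% | 1.17 | 9% | 14% |
| 1 | 1/4 = 25% | 1.35 | 23% | 41% |
| 2 | 2/5 = 40% | 1.70 | 63% | 90% |

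The nominal chance in that direction is 2.5%.

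**Step 4. Equal proportional loss.** Start from 6% vs 3% (OR 2.06) and remove the same share in both arms. At 10%, 5.4% vs 2.7% gives OR 2.06 and power 87%. At 20%, 4.8% vs 2.4% gives OR 2.05 and power 82% (1,000 per arm). The odds ratio barely moves; only power falls.

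**Step 5. Loss in the alert arm only.** If 10% of a counted 6% is not retained and control is unaffected, 5.4% vs 3% gives OR 1.85 in place of 2.06, and power 76% at 1,000 per arm.

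Bias in the odds ratio therefore needs a loss that differs by arm.

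**The case against.** The strongest reply is that this is a gap in wording with little consequence.

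- **Unsigned orders.** A reader might infer that the SAP scores an accepted but unsigned cart order as a success. The documents do not support that. The SAP's endpoint is a prescription placed; what goes into the cart is an order, and signing is the step that prescribes. Protocol 8.4 lists only signed prescriptions as outcome data. The SAP also uses *placed* for non-statin agents that are not order options in the protocol's example alert, where it reads simply as prescribed. This objection largely stands, and only an ambiguity remains.
- **Cut-off for cancellation.** A reader might infer that an order canceled months later turns a Yes into a No. The sentence before the counting rule in 8.1 sets a 24-hour measurement window, and the natural reading is status within it. This also stands in part: the text suggests the cut-off but does not state it.
- **Mechanism and size.** Clinicians need not accept at chart opening; they may acknowledge, and the example alert offers a 24-hour snooze. In the illustration, 1 extra point means that a quarter of counted interruptive-arm orders are not retained, with none added in control. No passage supports such a rate. This stands.
- **Existing data.** Protocol 8.3 already records acceptance and prescription time, so accepted-but-not-prescribed cases can be tabulated. That is true, but it does not identify orders signed and then canceled.

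What the reply does not remove is the conflict over canceled orders. The protocol defers analysis sets and covariates to the SAP but not the endpoint definition, so nothing says which text governs.

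**Conclusion.** The protocol and SAP give different rules for which orders count on the primary endpoint. The firm part is cancellation: Protocol 8.1 excludes canceled prescriptions, and Protocol 8.4 and the SAP do not. The missing assessment time and the double use of *placed* are lesser points.

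It is tempting to conclude that the interruptive effect will be overstated. The documents do not show this. They give no unsigned or canceled rates, and an equal proportional loss leaves the odds ratio at about 2.05 to 2.06. The figure of OR 1.35 with about a 23% chance of significance at 1,000 per arm (41% at 2,000) rests wholly on an assumed 1 extra point in one arm only. It shows that small unequal miscounts matter when planned rates are 3% and 6%; it does not estimate what will happen. The planned sample size reproduces and is not in dispute.

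This is an alignment that should be made before outcome data are extracted. It is not a demonstrated bias.

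**What to change.** Carry the protocol's rule into the SAP and Protocol 8.4 as one definition, applied identically in all arms: a statin prescription signed within 24 hours of the enrollment BPA firing and not canceled within that same 24-hour window, with cart orders never signed counted as No. Stating the window settles the cut-off that 8.1 only suggests.

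In addition:

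- replace *placed* with *signed* in the 12-month prescription endpoints;
- add order status and cancellation date and time to the data listed in Protocol 8.3 and 8.4;
- tabulate accepted-but-unsigned and canceled orders by arm, so that readers can see whether the rule mattered.

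The cost is a few sentences in each document and one extra EHR order-status field with its time stamp. The alert-arm rate may come out slightly lower than under a literal *placed* rule.

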- The analysis set will include all participants in the target population for the analysis of statin prescription placed within 24 hours (the primary endpoint), statin prescription placed within 12 months after enrollment BPA (a secondary endpoint), non-statin lipid lowering agent prescription placed within 12 months after enrollment (an exploratory endpoint), and new ASCVD event within 12 months of enrollment (an exploratory endpoint).
- For the analysis of the first LDL-C level measured during the follow-up (a secondary endpoint), statin prescription filling within 12 months of enrollment (an exploratory endpoint), and time from enrollment to statin prescription (an exploratory endpoint), the analysis set will include participants in the target population who do have the outcome measures but exclude patients whose outcomes are missing even after imputing the outcomes as described in the section, 'Handling Missing Data.'

Descriptive Analysis

General approach:

Categorical variables will be summarized using frequencies and proportions, and continuous variables will be described using means and standard deviations, as well as medians and interquartile ranges. The data also will be described graphically as needed. Missingness will be reported for each variable. No statistical comparisons between arms will be performed for these descriptive analyses.

Characteristics of the study sample:

Patient baseline demographic and clinical data as well as the provider information will be summarized overall and by intervention arm. The following variables will be described at time of enrollment:

• Patient sex (male, female, unknown)

PI: [name], MS

- Patient race (African American, Asian/Pacific Islander, Caucasian, Multiple, Native American, Other, Unknown)
- Patient self-reported ethnicity (Hispanic, Non-Hispanic, Unknown)
- Patient age (years)
- Patient comorbidities:
 - o Diabetes (Yes/No)
 - o ASCVD diagnosis (Yes/No)
 - o Congestive heart failure (Yes/No)
 - Hypertension (Yes/No)
 - o Peripheral artery disease (Yes/No)
 - o Stroke (Yes/No)
- Patient body mass index (BMI, kg/m²)
- Patient Charlson comorbidity index
- Type of patient statin therapy recommended to provider (moderate intensity, high intensity, high intensity and potential work up for LDL >= 190, low-dose statin for liver disease)
- Provider role (e.g., physician, physician assistant, resident physician, nurse practitioner)
- Prior statin prescription
- Visit type (in person or telemedicine)

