Patient age, sex, Charlson Comorbidity Index, type of patient statin therapy recommended to provider, baseline LDL-C level, ASCVD disease, diabetes, chronic kidney disease, prior statin prescription, visit type (in person or telemedicine), provider role, and time from enrollment to follow-up LDL-C level measurement.

Population-Level Summaries

Odds ratios (ORs) will be used for the analysis of binary (and ordinal) outcomes. For the analysis of the first LDL-C level measured during the follow-up, the estimates of mean differences in LDL-C levels, comparing interruptive reminder vs. no reminder arms, non-interruptive reminder vs. no reminder arms, and interruptive reminder vs. non-interruptive reminder arms will be used if a linear regress model is used. Hazard ratio (HR) will be used for the analysis of time to statin prescription.

Handling Missing Data

We do not expect missingness in our primary outcome and a secondary outcome of statin prescription within 12 months after BPA firing. Some missingness is expected for the first LDL-C level measured during the follow-up. For these missing outcomes, if a prior LDL-C level is available, the outcome will be imputed using the last known LDL-C level prior to the follow-up period; otherwise, the patient will be excluded in this analysis. For the exploratory outcomes, a complete case analysis will be performed without imputing the missing outcomes.

Missing covariates are not expected, or to be small percentage if occurs, which will be imputed using a single imputation. If missing data are substantial, multiple imputation will be used to handle missing covariates.

Intercurrent Events

To handle intercurrent event due to death or switching providers to other institutions, a whilealive strategy will be used.

Differential Treatment Effects

We will explore differential treatment effects for the primary endpoint only. Differential treatment effects will be explored by examining the interaction between the intervention arm

PI: [name], MS

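### The SAP does not say that never-prescribed patients count as No for 12-month statin filling, and its analysis set may drop them, turning the arm comparison into adherence among those prescribed

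*SAP*

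**What the plan says.** SAP, Exploratory Endpoints, item 2, defines the outcome as "A binary outcome of any statin prescription filled within 12 months of enrollment BPA firing (Yes/No"). SAP, Analysis Dataset, then sorts the endpoints into two sets.

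- The first bullet begins "The analysis set will include all participants in the target population for the analysis of statin prescription placed within 24 hours" and also covers 12-month prescription, non-statin agents and new ASCVD events.
- The second bullet covers the follow-up LDL-C, "statin prescription filling within 12 months of enrollment (an exploratory endpoint") and time to prescription. For these, "the analysis set will include participants in the target population who do have the outcome measures but exclude patients whose outcomes are missing", after any imputation described elsewhere.

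SAP, Handling Missing Data, provides no imputation for filling: "For the exploratory outcomes, a complete case analysis will be performed without imputing the missing outcomes". The same section says of the prescription outcomes: "We do not expect missingness in our primary outcome and a secondary outcome of statin prescription within 12 months after BPA firing".

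Protocol section 8.4 describes the fill data only as "Filling of statin prescriptions within 365 days after the intervention". It gives no denominator, data source or scoring rule. SAP, Primary Analysis, specifies a logistic regression by arm for the exploratory binary outcomes.

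**The concern.** A patient with no statin prescription has nothing to fill. The plan does not say whether that patient is a No or lacks the outcome measure, and the two choices answer different questions.

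If the patient is a No, the analysis compares randomized groups and asks whether the reminder format changes how many patients fill a statin. That is the exploratory aim in Protocol section 3.0. If the patient is excluded, the analysis is limited to those prescribed. Prescription happens after randomization and is what the reminder tries to change. The restricted comparison therefore takes out most of the mechanism under study, loses the protection of randomization, and becomes a comparison of adherence among prescribed patients.

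The Protocol's Blinding section says clinicians and investigators are not blinded. An open scoring rule could therefore be settled after results by arm have been seen.

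**Working it through.** **Plan's own figure.** The documents give no figure for filling. The one related calculation is the sample size for 3% vs 6% prescribing (SAP, Sample Size Considerations). With a two-sided 0.05 test, 90% power and pooled variance:

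n = [1.960 × √(2 × 0.045 × 0.955) + 1.2816 × √(0.03 × 0.97 + 0.06 × 0.94)]² / 0.03² ≈ 1,002 per arm, or 3,006 for three arms.

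This matches the plan. It concerns 24-hour prescribing and says nothing about filling at 12 months.

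**Inputs for the illustration.** From the plan: 1,000 patients per arm. Assumed, because the documents are silent: 12-month prescribing of 15% (control) and 20% (interruptive), and 80% of prescriptions filled. Ranges are given below. The same reasoning applies to any two arms whose prescribing rates differ.

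**Formulas.** Let m be the number prescribed and x the number with a fill, with subscript 1 for interruptive and 0 for control.

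- All patients: OR = [x₁/(1000 − x₁)] / [x₀/(1000 − x₀)]
- Prescribed only: OR = [x₁/(m₁ − x₁)] / [x₀/(m₀ − x₀)]

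If both arms have the same fill probability f, then x = f × m and the second formula becomes [f/(1 − f)] / [f/(1 − f)] = 1. The masking at equal fill is therefore exact and does not depend on the prescribing rates.

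**Results (control vs interruptive).**

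| Assumption | Prescribed | Fills | OR, all patients | OR, prescribed only |
|---|---|---|---|---|
| 80% filled in both arms | 150 vs 200 | 120 vs 160 | (160/840)/(120/880) = 1.40 | (160/40)/(120/30) = 1.00 |
| The 50 extra prescriptions filled 60% of the time | 150 vs 200 | 120 vs 150 | (150/850)/(120/880) = 1.29 | (150/50)/(120/30) = 0.75 |
| 70% control, 80% interruptive | 150 vs 180 | 105 vs 144 | (144/856)/(105/895) = 1.43 | (144/36)/(105/45) = 1.71 |

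In the first row the all-patient comparison (12% vs 16%) has power of about 73%. The restricted comparison has no effect to detect.

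In the second row the log odds ratio among prescribed patients has standard error √(1/150 + 1/50 + 1/120 + 1/30) = 0.261, so the 95% interval around 0.75 is about 0.45 to 1.25.

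**Range.** Control prescribing was varied from 10% to 20%, with 3 or 5 points added by the alert.

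- 80% fill throughout: the all-patient OR runs from 1.18 (160 vs 184 fills) to 1.57 (80 vs 120 fills). The prescribed-only OR is always 1.00.
- Extra prescriptions filled 50% to 60% of the time: the all-patient OR is 1.11 to 1.42 and the prescribed-only OR is 0.58 to 0.86.
- Fill lower still in the alert arm: both can fall below 1. At 15% vs 18% prescribed and 80% vs 60% filled, fills are 120 vs 108 and the ORs are 0.89 and 0.38.

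**The case against.** The best defence is that the endpoint definition already settles the matter. Any statin filled, Yes or No, is a question every enrolled patient can answer, and a patient with no prescription and no fill is naturally a No. The second bullet excludes only missing outcomes and never mentions being prescribed. Prescription status is expected to be complete, so never-prescribed patients are identifiable. Time to prescription sits in the same bullet and is to be analysed by Cox model and Kaplan-Meier curve, which normally keep patients without the event as censored. Having the measure need not mean having the event. The effect on prescribing would also remain visible in the 12-month prescription endpoint, and the SAP promises to report missingness by variable and to summarise endpoints by arm.

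Much of this stands. The restrictive reading is not the only one, and no section names the fill data source, so it cannot be asserted that fill data exist only for patients with a written prescription. What the defence does not explain is why filling alone among the binary endpoints was moved out of the all-participants set. The non-statin agent endpoint stayed there, and for it the absence of a prescription evidently counts as No. The grouping with time to prescription can be argued either way, and no sentence resolves it. Visible missingness would alert a reader to the problem but would not restore the randomized comparison.

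**Conclusion.** The point holds as an unresolved restriction on the analysis set. One plausible reading of the SAP drops never-prescribed patients from the fill analysis, and at equal fill rates that hides a real increase in fills completely (OR 1.40 becomes 1.00 in the illustration). The masking follows from algebra. Its size rests on assumed 12-month prescribing and fill rates.

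Three stronger conclusions that a reader might draw are not supported.

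- That the SAP plans to analyse prescribed patients only. It does not say so.
- That the sign will reverse. Reversal needs alert-prompted prescriptions to be filled less often, though not so much less that total fills also drop. The documents give no fill rates, and the illustrative 0.75 is imprecise. If fill is higher in the alert arm, both analyses point the same way.
- That 94% to 97% of patients would be lost. Those shares come from the 24-hour planning rates (100% − 6% and 100% − 3%) and do not describe a 12-month endpoint.

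The endpoint is one of four exploratory ones. The primary and secondary prescription analyses and the sample size are unaffected. Priority is low to moderate.

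**What to change.** In SAP, Analysis Dataset, move 12-month statin filling to the first bullet, so that all participants in the target population are analysed. Add a scoring rule: Yes for any recorded statin fill within 12 months, whoever prescribed it, and No for every patient without a recorded fill, including those never prescribed. Exempt this endpoint from the complete-case sentence in Handling Missing Data. Otherwise prescribed patients with unobtainable fill status would still be excluded, and exclusion would again depend on prescription.

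Report by arm the number of prescribed patients whose fill status could not be obtained, and add a sensitivity analysis that scores them all Yes. Give the fill rate among prescribed patients as a descriptive figure only.

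The cost is a few sentences and one small table, with no new data collection. The downside is that fills not captured in the data count as No. That lowers the observed fill rates, and if capture differed by arm it could bias the comparison. The sensitivity analysis addresses this only for prescribed patients.

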### **Secondary Outcomes Analysis**

Study Protocol. Version August 9, 2024

Full Study Title: Interruption versus Non-Interruption Reminders for Statin tHerApy in Primary Care (INIRSHA-PC). A Randomized Trial.

Primary Investigator: [name], MS

The secondary outcomes include a binary outcome of statin prescription within 12 months post-randomization and first post-randomization LDL-C level. To compare each outcome between the interruptive reminder arm, non-interruptive reminder arm, and control arm, a logistic regression will be used to analyze the binary outcome of statin prescription within 12 months post-randomization while a linear regression analysis will be performed to compare LDL-C level between the arms. If the distribution of LDL-C levels is highly skewed, an ordinal logistic regression analysis will be used in place of a linear regression. The analysis set for the secondary outcomes will be described in the SAP.

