Description of the endpoints:

All the endpoints will be summarized overall and by intervention arm.

Primary Analysis

General approach:

All primary analyses will be performed without covariate adjustment as the study interest lies in estimating the overall intervention effects observed in a diverse patient population in their usual clinical settings. To account for potential imbalance in covariate distribution across arms, secondary analyses will be performed with *a priori* selected covariate adjustment. All analysis results will be reported with point estimates and 95% confidence intervals (CIs). No adjustments for multiplicity will be made.

Analysis of the primary endpoint:

Statin prescription within 24 hours of enrollment BPA firing will be compared between intervention arms using a logistic regression with indicator variables for intervention arms.

Analysis of secondary endpoints:

Statin prescription placed within 12 months after enrollment BPA firing will be analyzed using a logistic regression. For the first LDL-C level measured during the follow-up, a linear regression analysis will be performed with intervention arm indicator variables. If the distribution of LDL-C levels is highly skewed, an ordinal logistic regression analysis will be used in place of a linear regression.

Analysis of the exploratory endpoints:

A logistic regression will be performed to compare the binary outcomes between intervention arms. Time from enrollment BPA firing to statin prescription will be compared between

PI: [name], MS

intervention arms using a Cox proportional hazard model and the differences in the outcome between arms will be visualized using Kaplan-Meier curve.

Secondary Analysis

The covariate adjusted analysis will be performed for the primary and the secondary outcomes using the same regression analysis methods with adjustment of the following covariates.

Covariates for the analysis of statin prescription (the primary endpoint and a secondary endpoint):

Patient age, sex, Charlson Comorbidity Index, type of patient statin therapy recommended to provider, baseline LDL-C level, ASCVD disease, diabetes, chronic kidney disease, prior statin prescription, visit type (in person or telemedicine), and provider role.

Covariates for the analysis of the first LDL-C level measured during the follow-up:

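### The main LDL-C analysis leaves out baseline LDL-C, which costs precision that a linear model could recover without changing what is estimated

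*SAP*

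**What the plan says.** The SAP (Primary Analysis, analysis of secondary endpoints) sets the main LDL-C model: "For the first LDL-C level measured during the follow-up, a linear regression analysis will be performed with intervention arm indicator variables". If LDL-C is highly skewed, ordinal logistic regression replaces it. Protocol 12.0, Secondary Outcomes Analysis, agrees: "a linear regression analysis will be performed to compare LDL-C level between the arms".

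Leaving out covariates is deliberate. Under General approach the SAP says: "All primary analyses will be performed without covariate adjustment as the study interest lies in estimating the overall intervention effects". To deal with possible imbalance between arms, "secondary analyses will be performed with *a priori* selected covariate adjustment".

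The covariate list for that secondary LDL-C model includes "type of patient statin therapy recommended to provider, baseline LDL-C level, ASCVD disease, diabetes, chronic kidney disease" and ends with "provider role, and time from enrollment to follow-up LDL-C level measurement".

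Three other provisions bear on the point:
- LDL-C is among the baseline data (Protocol 8.2), and the last LDL-C is used for eligibility (Protocol 5.2).
- The SAP's summary measure for LDL-C under the linear model is the mean difference between arms (Population-Level Summaries).
- A missing follow-up LDL-C is replaced by the last value known before the follow-up window, where one exists (Handling Missing Data).

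**The concern.** A patient's earlier LDL-C is normally a strong predictor of the later one. A model with arm indicators only treats that predictable variation as noise, so the interval for the arm difference is wider than it needs to be.

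The SAP's reason for not adjusting has force for odds ratios and hazard ratios, where adding covariates can change the quantity being estimated. It has none for a difference in means from a linear model: under randomization the adjusted and unadjusted models target the same overall difference.

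The secondary model does not fully fill the gap. Time to the follow-up test is fixed only after randomization and could depend on arm, for instance if starting a statin prompts an earlier test. As written, the plan therefore has no LDL-C estimate adjusted for baseline variables alone. LDL-C is also absent from the SAP's list of baseline variables to be described by arm, so a chance imbalance might go unseen.

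What is at stake is the precision of a secondary endpoint whose plausible effect is small, because the reminder is expected to change prescribing in only a few patients per hundred.

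**Working it through.** **The plan's own figure.** The documents give no SD, sample size or power for LDL-C. The arm size and prescribing difference used below come from the primary-endpoint calculation, so that is checked first. For 3% against 6%, two-sided 0.05, 90% power and pooled variance:

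n = [1.960·√(2·0.045·0.955) + 1.282·√(0.03·0.97 + 0.06·0.94)]² / 0.03² = (0.5746 + 0.3747)² / 0.0009 ≈ 1,001.4, rounded up to 1,002 per arm.

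This matches the stated 1,002.

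**Inputs from the documents.** 1,000 per arm planned and 2,000 per arm at most; a 3-point prescribing difference.

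**Assumed inputs (not in the documents).** LDL-C SD 35 mg/dL, equal at baseline and follow-up; baseline to follow-up correlation r of 0.4 to 0.7; LDL-C fall of 30 to 60 mg/dL per additional treated patient.

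**Plausible effect.** 0.03 × 30 = 0.9 mg/dL to 0.03 × 60 = 1.8 mg/dL. The worked example uses 0.03 × 50 = 1.5 mg/dL.

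**Formulas.**
- Unadjusted SE = SD·√(2/n) = 35·√(2/1000) = 1.57 mg/dL.
- Adjusted SE = 1.57·√(1 − r²).
- Equivalent sample-size factor = 1/(1 − r²), which does not depend on SD or n.
- Power at effect d = Φ(d/SE − 1.96) + Φ(−d/SE − 1.96).
- Chance of a wrong-signed estimate = Φ(−d/SE).
- SD of the part of a chance baseline difference that reaches the unadjusted estimate, for measured outcomes = r × 1.57.

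| Model | SE (mg/dL) | Patients factor | Power at 1.5 | Wrong sign | Carried imbalance, SD (mg/dL) |
|---|---|---|---|---|---|
| Unadjusted | 1.57 | 1.00 | 16% | 17% | r × 1.57 |
| Adjusted, r = 0.4 | 1.43 | 1.19 | 18% | 15% | 0.63 removed |
| Adjusted, r = 0.5 | 1.36 | 1.33 | 20% | 13% | 0.78 removed |
| Adjusted, r = 0.6 | 1.25 | 1.56 | 22% | 12% | 0.94 removed |
| Adjusted, r = 0.7 | 1.12 | 1.96 | 27% | 9% | 1.10 removed |

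The last column is not an extra error. It is the part of the unadjusted SE that adjustment takes out: at r = 0.7, √(1.57² − 1.12²) ≈ 1.10.

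**At the maximum size.** With 2,000 per arm the unadjusted SE is 35·√(2/2000) = 1.11. Power at 1.35 mg/dL (0.03 × 45) is 23% unadjusted, against 29% at r = 0.5 and 40% at r = 0.7.

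**Effect of carrying values forward.** If the outcome is replaced by the baseline value itself, the whole baseline difference passes through for that patient. A simulation (4,000 runs, 1,000 per arm, SD 35, fall of 45 mg/dL per treated patient) gave these ratios of adjusted to unadjusted SE:

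| Outcomes carried forward | r = 0.5 | r = 0.7 |
|---|---|---|
| 0% | 0.87 | 0.74 |
| 30% | 0.76 | 0.63 |
| 50% | 0.68 | 0.55 |

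So the SAP's outcome-imputation rule makes baseline adjustment more useful. Carrying values forward also shrinks the mean difference itself, equally with and without adjustment. That is a separate question.

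**The case against.** The strongest reply is that the plan already covers this. Adjusted analyses of the secondary outcomes are pre-specified, their stated purpose is to address imbalance, baseline LDL-C is on the list, and all results are to be reported with intervals. A baseline-adjusted LDL-C estimate will therefore appear beside the unadjusted one. That is largely fair: the dispute is about which analysis leads, and about one post-randomization covariate in the other. Deleting that covariate would by itself yield a clean adjusted estimate. What remains is that the main result gives up precision for a reason that does not apply to it.

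A reader might go further and infer that the unadjusted result is biased, or that it carries the full chance baseline imbalance (SD 1.57 mg/dL), about as large as the effect itself. The documents do not support that. The estimate is unbiased over randomization and its interval already allows for this variation. For measured outcomes only about a fraction r carries through, 0.63 to 1.10 mg/dL here. All of it carries through only where the baseline value stands in for the outcome, and the plan does not say how often that will be.

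Three further objections stand as limits:
- SD, correlation and LDL-C fall are assumptions. Known LDL-C below 100 mg/dL and a lipid panel within 3 months are exclusions, so baseline values are range-restricted and not recent. Both could lower r. At r = 0.3 the gain is only 1/(1 − 0.09) = 1.10, or 10% more patients.
- The effect uses the 24-hour prescribing difference, whereas LDL-C is measured between 30 days and 12 months and alerts can repeat. With a 6-point difference the effect would be 1.8 to 3.6 mg/dL and imbalance would matter less.
- The same-quantity argument fails for the ordinal fallback, where adjusted and unadjusted odds ratios have different targets.

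**Conclusion.** The point holds as one of lost precision. The main LDL-C model omits a baseline value that is already collected, and in the linear model including it would not change the quantity estimated. Under r of 0.4 to 0.7 the gain equals about 19% to 96% more patients; this range depends on r alone. The SE figures (1.57 down to 1.43–1.12 mg/dL) also rest on the assumed SD of 35 and 1,000 patients per arm.

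Adjustment does not rescue the endpoint. At 1.5 mg/dL and 1,000 per arm, power rises only from 16% to between 18% and 27%. The possible distortion from conditioning on time to test has not been quantified. The primary endpoint and its conclusion are unaffected. The change is worth making because it is nearly free.

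**What to change.** In the SAP, define the main linear LDL-C model as arm indicators plus the last LDL-C before enrollment, without the time-to-test term. Handle patients with no pre-enrollment LDL-C by the SAP's existing rule for missing covariates (single imputation, or multiple imputation if missingness is substantial). Keep the unadjusted mean difference as a supportive result. State that the reasoning applies to the linear model only, and say separately what the ordinal fallback will adjust for. Align Protocol 12.0, Secondary Outcomes Analysis.

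Leave the outcome-imputation rule and the LDL-C analysis set as they are for this purpose; any change to them needs its own argument.

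The cost is wording in two documents, preferably settled before LDL-C is compared by arm. No new data are needed.
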